3.5 If applicable, please select the Designated Department Approval(s)

Add the name of the individual authorized to approve and sign off on this protocol from your Department (e.g. the Department Chair or Dean).

4.0

Initial Screening Questions

Updated June 2017

4.1 * PROJECT SUMMARY: (REQUIRED) Give a brief overview of this project (250 words or less). Tell us what this study is about, who is being studied, and what it aims to achieve. If you have an NIH Abstract, paste it here: Click on the orange question mark to the right for more detailed instructions.

This is a randomized controlled trial (RCT) exploring the effect of using the Livongo Health Diabetes Management Program versus standard blood glucose (BG) monitoring on glycemic control, as measured by change in hemoglobin A1c (A1c), in adults with diabetes over the course of 6 months. Secondary outcomes include frequency of BG monitoring, frequency of BG measurements outside of the target range, change in diabetes distress, and number of self-reported emergency room visits or hospitalizations.

4.2 * HUD DEVICE: (REQUIRED) Does this application involve a Humanitarian Use Device (HUD):

- No
- Yes, and it includes a research component
- Yes, and it involves clinical care ONLY

4.3 * TYPE OF RESEARCH: (Click the Help link for definitions and guidance): (REQUIRED)

- Biomedical research

- Social, behavioral, educational, and/or public policy research
- Hybrid - includes aspects of BOTH types of research (check this option if your research is mainly social/behavioral but also involves specimen collection or blood draws to look at biological measures)

4.4 * SUBJECT CONTACT: (REQUIRED) Does this study involve ANY contact or interactions with participants:

- Yes (including phone, email or web contact)
- No (limited to medical records review, biological specimen analysis, and/or data analysis)

4.5 * RADIATION EXPOSURE: Does your protocol involve any radiation exposure to patients/subjects EITHER from standard care OR for research purposes (e.g., x-rays, CT-scans, DEXA, CT-guided biopsy, radiation therapy, or nuclear medicine including PET, MUGA or bone scans): (REQUIRED)

- Yes No

4.6 * RISK LEVEL: (REQUIRED) What is your estimation of the risk level, including all screening procedures and study activities (Help Text updated 9/13):

- Minimal risk
- Greater than minimal risk

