If some of the activities would occur even if the person were not in the study, as in the case of treatment or tests performed for diagnostic purposes, clearly differentiate between those activities that will be done solely for research purposes and those that are happening as part of routine care.

Please call our office at [contact] and ask to speak to someone on the Expedited Review team if you need help differentiating between what parts are research and what parts aren't.

1. Surveys and Measurements

- All study participants may complete surveys via their personal iOS smartphone device on: study qualification (intake survey/eligibility screener discussed further in Section 10.3), diabetes status (initial diabetes survey), physical activity (iPAQ), quality of life (SF-12), vitals (attached), demographics (attached) hospitalizations and interaction with health care provider (attached), and diabetes distress (attached). Most survey data will be collected at 1, 3, and 6 months. There will also be Weekly Engagement surveys (attached) which will be two simple questions each week. At the end of the study, a Feedback survey (attached) will ask participants about their study experiences. Surveys will each have a simple description to introduce participants to the survey they are being asked to take (document attached). These surveys will be administered through the Eureka mHealth Research Platform, the study's main tool for data collection, data storage, and study management. Specific usability assessments that are native to the Livongo or iHealth platform may also be shown through the device to the participants in order to gather user feedback information.
- After qualifying and providing consent to participate in the study, participants will be referred to a convenient lab for establishing hemoglobin A1c (A1c) levels and lipid panel levels. A1c labs will be collected at months 1 (baseline), 3, and 6 (closeout). For each A1c lab, 1mL of blood will be drawn. Lipid panels (total cholesterol, LDL, HDL, and triglycerides) will be collected at months 1 (baseline) and 6 (closeout). For each lipid panel lab, 1mL of blood will be drawn.

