- As an alternative to visiting a lab, participants will have the option of using a Home Access Health Co. Mail-in Laboratory Test Kit to collect a sample for establishing A1c and lipid panel levels. Just as if they were to visit a local lab, these samples will be collected at months 1 (baseline), 3, and 6 (closeout). At months 1 and 6, participants will use a professional use finger prick blood collection kit to collect 75 microliters of blood. The Mail-in Lab Test is coded for A1c and complete lipid panel testing. This professional use kit requires a requisition for the participant, which will be provided by Home Access physicians. At month 3, participants will use an FDA approved direct-to-consumer A1c kit to collect 35 microliters of blood for A1c levels only. No physician authorization is required for this kit. When time for each blood draw at months 1, 3, and 6, participants will be sent the appropriate kit that will include everything

necessary for successful collection, packaging, and mailing of specimen, including a cover letter from the SUGAR Study Team (attached). All samples will be mailed to the Home Access Health laboratory for testing.

- Participants are strongly encouraged to be consistent with whichever method they choose. This means that if their first blood draw occurs at a Quest Labs, we would like them to complete their second and third blood draws at a Quest Labs as well. If they choose to use a home kit for their first blood draw, we would like them to use a home kit for their second and third blood draws if possible.
- If a participant wishes to obtain a copy of the lab results, they may email the study coordinator to request a copy at [contact]. Their results will be sent through the study coordinator's UCSF email securely with "ePHI:" or "Secure:" in the subject field. We have indicated in the consent form how a participant may retrieve their lab results and have also included the statement that we do not provide a clinical interpretation of their data from the study or provide medical advice. Additionally, we have included language indicating participation in this study does not in any way substitute for professional medical advice, diagnosis, or treatment that their doctor or other healthcare provider may give them. If they think they may have a medical emergency, they are recommended to call their doctor or notify emergency services.

2. Randomization

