- Once the baseline A1c value is obtained, the patient will be randomized (block randomization by diabetes type).

3. Device Usage

- After randomization, participants will receive either the Livongo Health system or the iHealth glucose meter by mail.
 - If a participant is randomized to the iHealth treatment group, participants will download the iHealth iOS application (iHealth Gluco-Smart) and receive an iHealth blood glucose meter in the mail. Participants will link the iHealth application with a mobile version of the Eureka mHealth Research Platform.
 - If a participant is randomized to the Livongo system treatment group, the participant will receive the Livongo blood glucose meter device in the mail, create a Livongo account, and link their Livongo account with the Eureka mHealth Research Platform.
- Livongo- or iHealth-specific instructions will be provided with each meter and a study coordinator will be available to answer study participant questions about using the BG meters. Participants may be referred to Livongo or iHealth customer service for technical support, if needed.
- Participants will not be given specific instructions on how often to check their BG, or how often they should use the Livongo system or iHealth glucose meter as a part of this study. This is done in order to determine the uptake of the intervention and resulting behavior without outside prompting.
- Participants will either use the Livongo system or the iHealth glucose meter for 6 months from the time of enrollment in the study.

4. Messaging/Reminders

- Participants who have been mailed a BG meter but are not using the device after two weeks will be contacted by in-app push notifications, text messages, email or a phone call for device setup and/or assistance.
- Participants will also receive reminders to complete study activities via in-app push notifications, text messages, email or a phone call.
- Two weeks prior to the end of the study period, participants will be contacted by email and/or receive in-app push notifications to remind them to complete their A1c measurement and closeout surveys.

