- Other (describe below):

7.14 * SPECIMENS ARE: (check all that apply): (REQUIRED)

- Leftover specimens from a clinical diagnostic or therapeutic procedure
- Specimens collected for research purposes only (including extra samples taken during a clinical procedure)
- Other

7.15 * DESTINATION: Specimens will ultimately be stored (check all that apply): (REQUIRED)

Outside Entity:

- Cooperative group bank
- NIH
- Other university
- Industry sponsor
- Other

UCSF:

- UCSF repository/bank being established under this protocol
- Existing UCSF specimen repository/bank with CHR approval
- Other location at UCSF (please describe)

Provide the name of the bank and iRIS approval number (if not being banked at UCSF under this protocol). If you checked 'Other,' please provide the location or lab:

The blood samples we draw (through Quest Labs or Home Access mail-in kit) will be used for analysis of the participant's blood sugar levels. The study does not intend to store or bank any of the samples after analysis. The participants will be sent their requisition in a secure email or through a secure download link to bring with them to the lab if they miss their selected date.

7.18 * FUTURE SPECIMEN USE: Will any specimens or portions of specimens be retained after the study is over for possible use in future research studies: (REQUIRED)

- Yes
- No

7.20 * CLINICAL FOLLOW-UP DATA: Will clinical follow-up data be linked to specimens (i.e., will medical record information continue to be abstracted after the specimen is collected): (REQUIRED)

- Yes
- No

Provide duration of follow-up or 'indefinitely':

7.25 STATISTICAL METHODS: Briefly summarize the methods and types of analyses that will be performed:

Descriptive statistics (t-tests for continuous variables and chi-squared tests for dichotomous variables) will be used to compare demographic, clinical, and socioeconomic variables. The primary outcome measure is change in A1c. Data will be analyzed as a comparison between experimental and control groups. Data may also be stratified by duration of diabetes and baseline HbA1c (< 7.0% vs 7.0). Methods for analyzing longitudinal data (mixed-effects linear regression models or generalized estimating equations) will be used to look for the effect of using Livongo on change in A1c, adjusting for possible confounding variables. Similar models will be used to examine secondary outcomes.

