- Not be able to provide consent (emergency waiver of consent - allowed for minimal risk research or greater than minimal risk research with an approved community consultation plan)
- Not know about the study, as in the case of chart reviews or observations of public behavior (waiver of consent)
- Other method (describe below)

10.8 * CONSENT PROCESS: Describe the process for obtaining informed consent, including details such as who will have the consent discussion and when participants will be asked to sign the consent form in relation to finding out about the study: (REQUIRED) We encourage researchers to review our guidance on obtaining and documenting informed consent.

- If there are multiple groups being consented differently, provide details about the consent process for each group.
- If you are relying on **verbal or implied consent**, provide details about how that will happen.
- For studies using online recruitment and consent or consent via mail, provide details here.

Informed consent will be obtained electronically through the mobile-based study workflow. In order to ensure that participants are thoroughly informed, we will implement the following series of screens:

1. An eligibility screen with the inclusion and/or exclusion criteria; participants can only proceed if they are deemed eligible.
2. A summary screen with the most important aspects from the complete informed consent form (ICF).
3. The complete SUGAR ICF; participants are only eligible to consent after they scroll through the entire document (button won't activate otherwise).
4. At any point in the SUGAR study, participants can contact a SUGAR study coordinator or team member to address any questions.

10.10 * DECEPTION: Does this study rely on some deception or misinformation about what the researchers are observing to get valid data? (REQUIRED)

Yes No

10.13 TIME: What is the estimated time commitment for participants (per visit and in total):

Total duration of participation in the study is 6 months from date of submitting their baseline hemoglobin A1c lab. We estimate the following time commitments:

- Consent process: 5 minutes
- Baseline surveys: 12 minutes
- HbA1c and Lipid Panel test: At local lab: 5-10 minutes (plus travel time to the lab) x 3 (baseline, month 3, and 6 months/closeout). Using Home Kit: 15 - 20 minutes (no travel time to lab) x 3 (baseline, month 3, and 6 months/closeout)
- Use of the Livongo system vs control meter: 5-15 minutes per day

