- Follow-up surveys: 15 minutes x 2 (3 months and 6 months)

IMPORTANT TIP: Ensure this information is consistent with the information provided in the consent form.

10.16 OTHER ALTERNATIVES: Describe other alternatives to study participation, if any, that are available to prospective subjects:

Participants can choose to not participate or withdraw at any point in the study.

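### Does labelling the baseline A1c draw as month 1 leave the primary change measured over 5 months instead of 6?

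*Combined protocol and SAP*

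**What the plan says.** Several sections of the combined document describe the timing.

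- **7.9, Surveys and Measurements, lab route:** "A1c labs will be collected at months 1 (baseline), 3, and 6 (closeout". The home-kit route repeats these labels, and dispatch follows them: "When time for each blood draw at months 1, 3, and 6, participants will be sent the appropriate kit".
- **7.9, Device Usage:** "Participants will either use the Livongo system or the iHealth glucose meter for 6 months from the time of enrollment in the study".
- **7.9, Messaging/Reminders:** "Two weeks prior to the end of the study period, participants will be contacted by email".
- **10.13, Time:** "Total duration of participation in the study is 6 months from date of submitting their baseline hemoglobin A1c lab". The same section lists three lab tests (baseline, 3 months, closeout at 6 months), one set of baseline surveys, and "Follow-up surveys: 15 minutes x 2 (3 months and 6 months".
- **4.1, Project Summary:** change in A1c is assessed "in adults with diabetes over the course of 6 months".
- **7.25, Statistical Methods:** "The primary outcome measure is change in A1c", with a mixed-effects or GEE model and no named time point.

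**The concern.** The primary outcome is a change, so its interval is part of its definition. If month 1 is elapsed time, closeout falls 5 months after baseline and the middle draw 2 months after. Under 10.13 the intervals are 6 and 3 months. The device-use sentence counts from enrolment, which is not defined and need not coincide with the baseline lab. Kit dispatch and the closeout reminder depend on the calendar, so two coordinators following different sections could request the closeout sample a month apart. Section 7.25 does not settle it. At stake would be a blurred estimand, some dilution of the effect if benefit is still growing at month 5, and uncertain time coding in the longitudinal model.

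**Working it through.** **Step 1: the plan's own figures.** Section 9.3 gives a difference of 0.5, SD 1, two-sided alpha 0.05 and 80% power.

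- n per group = 2(1.960 + 0.842)² × (1/0.5)² = 62.8, so 63, as stated. The exact t-test version gives 63.8, so 64.
- Minimum detectable difference at 150 per arm = (1.960 + 0.842) × √(2/150) = 0.323 for 80% power (stated 0.33), and (1.960 + 1.282) × √(2/150) = 0.374 for 90% (stated 0.38).

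Follow-up time appears in none of these formulas, so the stated N is the same under either reading.

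**Step 2: the two readings.** Elapsed time gives 6 − 1 = 5 months to closeout and 3 − 1 = 2 to the middle draw. A slot label gives 6 − 0 = 6 and 3 − 0 = 3.

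**Step 3: which reading the documents support.**

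- The lab schedule attaches the word baseline to month 1. An elapsed month needs an earlier time zero, and none is defined. Under 7.9 participants are referred for the lab test once they have qualified and consented, and randomisation follows the baseline result. No one-month wait is described.
- Count the occasions. Section 7.9 puts most surveys at months 1, 3 and 6, which is three. Section 10.13 lists one baseline set plus two follow-ups, also three. The month-1 survey is therefore the baseline survey.
- Section 13.3 pays $25 for each of three lab tests, at baseline, month 3 and closeout (3 × $25 = $75). No separate month-1 test exists.
- Section 7.6 likewise treats month one as the baseline when it describes the preliminary data. That shows usage and is not proof.
- Section 10.13 is the only place that ties the duration to a defined event, the baseline lab. Section 4.1 agrees with its 6 months.

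**Step 4: the enrolment clock.** The sentence on enrolment governs device use and not the A1c schedule. If closeout were nevertheless timed from consent, the A1c interval would be 6 months minus the lag from consent to the baseline lab. The documents give no lag. An assumed 0 to 1 month returns the same range of 5 to 6 months.

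**Step 5: size if the 5-month reading were followed.** The documents give no time course for the effect, so the share of a 6-month effect present at 5 months is assumed. It is 5/6 = 0.833 for linear accrual. For an exponential approach with time constant τ it is (1 − e^(−5/τ))/(1 − e^(−6/τ)), which is 0.894 at τ = 6 months, 0.938 at τ = 3 and 0.996 at τ = 1. Power is from the noncentral t with SD 1:

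| Per arm with closeout A1c | Difference 0.500 | Difference 0.417 (linear, worst case) |
|---|---|---|
| 150 | 99.1% | 94.9% |
| 120 (assumed 20% loss) | 97.1% | 89.5% |
| 105 (assumed 30% loss) | 95.0% | 85.2% |

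At 150 per arm the difference could shrink to 0.323/0.5 = 65% of its planned size before power fell to 80%. One month out of six would have to remove over a third of the effect.

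**Step 6: bias and the model.** The baseline draw is taken before assignment and the same schedule serves both arms, so the interval does not depend on arm as planned. If visit is a categorical factor, month labels do not enter the model. If time is linear, coding 1/3/6 instead of 0/3/6 changes the slope estimate, but with no treatment effect the arm-by-time term is zero under either coding.

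**The case for a change.** The strongest case for acting is that this is not a single slip. The month-1 label recurs for lab A1c, lipids, home kits and dispatch, and the survey sentence gives 1, 3 and 6 months without marking the first as baseline. Nor do the labels fit one counting scale: if baseline is the first study month, a draw three elapsed months later would be month 4. Whoever programs dispatch has to interpret the text. The interval of a primary endpoint is a core item, and a wording correction would cost almost nothing.

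Much of this stands. The labels are inconsistent, enrolment is undefined, and 7.25 leaves the time point to 4.1. At the bare 63 per group, linear accrual would cut power from 80% to 65% (normal approximation), so the point would matter in a trial of that size. This one plans 150 per arm.

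What does not stand is the step from inconsistent labels to a real 5-month endpoint. That needs a time zero the documents never mention. Linear accrual also has little behind it: 9.3 attaches no horizon to its 0.5, and the evidence it lists includes falls of 0.4 at 3 months (7.9 to 7.5) and 0.55 at 6 months in adults (8.4 to 7.85), and a between-group difference of 0.50 at 12 months (−0.35 against +0.15). Those studies differ in design, but they do not suggest an effect growing in proportion to time. The unnamed time point in 7.25 would remain with perfect month labels, and the 6-month horizon in 4.1 gives the sensible reading.

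**Conclusion.** The inconsistency is clerical and calls for no change to the plan. Read together, 4.1, 10.13 and 13.3 give one schedule (baseline, 3 months, 6 months), and an analyst would take the primary change as running to the 6-month closeout. The interval from baseline can be computed from lab dates, on the assumption that these are kept, as counting from the baseline lab in 10.13 requires. The stated N is unaffected, and the ambiguity does not favour either arm. Even if the 5-month reading were followed, power for the planned difference stays between 95% and 99% at 150 per arm, and at 85% or more with an assumed 30% loss. These figures rest on the plan's SD of 1, on treating its 0.5 as a 6-month effect, and on accrual no slower than linear.

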6.0 Sites, Programs, Resources, and External IRB Review

6.1 UCSF AND AFFILIATED SITES (check all that apply):

- UCSF (including Laurel Heights and all the other sites outside the main hospitals)
- Parnassus
- Mission Bay
- China Basin
- Mount Zion
- Helen Diller Family Comprehensive Cancer Center
- Langley Porter Psychiatric Institute
- San Francisco General Hospital (SFGH)
- SF VA Medical Center (SF VAMC)
- Blood Centers of the Pacific (BCP)
- Blood Systems Research Institute (BSRI)
- Fresno Community Medical Center
- Gallo
- Gladstone
- Jewish Home
- Institute on Aging (IOA)
- SF Dept of Public Health (DPH)

6.2 LOCATIONS: At what locations will study visits and activities occur:

This is a remote and mobile-based study. Due to the nature of this study, there is the potential that participants from all over the United States may be recruited.

6.3 OFF-SITE PROCEDURES: Will any study procedures or tests be conducted off-site by non-UCSF personnel:

Yes No

Please identify which procedures may be done off-site:

Participants will either be directed to a nearby Quest Labs to get their hemoglobin A1c and lipid panel labs done, OR be sent a mail-in lab test kit (Home Access Health Corporations) for them to provide a blood sample at home. If participants choose to use the Home Access mail-in lab kit rather than visit a lab, their sample will be shipped (using the shipping materials provided) to the Home Access centralized lab for testing and determination of hemoglobin A1c and lipid panel levels.

6.4 RESEARCH PROGRAMS: Check any UCSF research programs this study is associated with:

- Cancer Center
- Center for AIDS Prevention Sciences (CAPS)
- Global Health Sciences
- Immune Tolerance Network (ITN)
- Neurosciences Clinical Research Unit (NCRU)
- Osher Center
- Positive Health Program

6.5 * CTSI CRS SERVICES: (REQUIRED) Will this study be carried out at one of the **UCSF Clinical Research Services (CRS)** units or utilize **CRS services**:

- Yes
- No

6.6 * MULTI-CENTER TRIAL: (REQUIRED) Is this a multicenter research trial? By multi-center trial, we mean a study where the protocol is developed by an industry sponsor, consortium, a disease-group, etc., who then selects sites across the nation or in different countries to participate in the trial. The local sites do not have any control over the design of the protocol.

- Yes
- No

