9.0 Sample Size and Eligibility Criteria

9.1 ENROLLMENT TARGET: How many people will you enroll:

300

If there are multiple participant groups, indicate how many people will be in each group:

Livongo Health system (experimental group) - 150
iHealth glucose meter (control/standard group) - 150

9.3 SAMPLE SIZE JUSTIFICATION: Explain how and why the number of people was chosen. For multi-site studies, this is referring to the number that will be enrolled across all sites:

- Sample size:
 - *Null Hypothesis:* There is no association between use of Livongo and change in A1c.
 - *Alternative Hypothesis:* (two-sided): The use of Livongo is associated with change in A1c.

- Effect size (t-test) = 0.5%
- Evidence:
 - A1c decreased from 7.9% to 7.5% in 3 month study of mobile phone-based data service (Kollman, et al., 2007, J Med Internet Res, 9:e36)
 - A1c decreased from 8.4% to 7.85% (adults) and 8.52 to 8.06% (children) in 6 month study using a multi-access diabetes management service (Lanzola, et al., 2007, J Diabetes Sci Technol, 1:730-7)
 - Difference in change in A1c -0.35 (intervention) vs +0.15 (control) after 12 months of using an automated diabetes management system (wireless glucose transfer) (Toscos, et al., 2012, Diabetes Care, 35:498-502)
- Standard deviation = 1% (based on the above publications)
- Standardized effect size = E/S = 0.5
- Using a two-sided t-test of 0.05 and power of 80%, n=63 participants per group

We anticipate that we will be able to recruit 300 participants (150 in each arm). Using the above parameters, the study would have 80% power to detect a minimum effect size of 0.33% (and 90% power to detect a minimum effect size of 0.38%).

9.4 * PARTICIPANT AGE RANGE: Eligible age ranges: (REQUIRED)

- 0-6 years
- 7-12 years
- 13-17 years
- 18-64 years
- 65+

9.5 * STUDY POPULATIONS: Data will be collected from or about the following types of people (check all that apply): (REQUIRED)

- Inpatients
- Outpatients
- Family members or caregivers
- Providers
- People who have a condition but who are not being seen as patients
- Healthy volunteers
- Students
- Staff of UCSF or affiliated institutions
- None of the above

9.6 * SPECIAL SUBJECT GROUPS: Check the populations that may be enrolled: (REQUIRED)

- Children / Minors
- Subjects unable to consent for themselves
- Subjects unable to consent for themselves (emergency setting)
- Subjects with diminished capacity to consent
- Subjects unable to read, speak or understand English

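### Does letting participants choose and switch between lab and home A1c collection require a collection-method term in the primary model?

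*Combined protocol and SAP*

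**What the plan says.** Section 6.3 gives the two routes. "Participants will either be directed to a nearby Quest Labs to get their hemoglobin A1c and lipid panel labs done", or they are sent a Home Access kit and post the sample to that company's laboratory.

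Section 7.9, item 1, leaves the choice to the participant and asks for consistency: "Participants are strongly encouraged to be consistent with whichever method they choose". For home users the request is softened: "we would like them to use a home kit for their second and third blood draws if possible". The home kit also changes by visit. "At months 1 and 6, participants will use a professional use finger prick blood collection kit", whereas "At month 3, participants will use an FDA approved direct-to-consumer A1c kit". All home samples go to one laboratory. Under item 2 of the same section, randomisation follows the baseline A1c result, so the first route is used before allocation.

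Section 7.25 states: "The primary outcome measure is change in A1c". Mixed-effects models or generalized estimating equations "will be used to look for the effect of using Livongo on change in A1c, adjusting for possible confounding variables". It mentions duration of diabetes and baseline HbA1c as possible strata. It does not mention collection method, a rule for switchers or a sensitivity analysis by route.

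**The concern.** The primary outcome is a difference between two measurements on the same person. A systematic offset between a venous draw at one company and a finger-prick sample at another cancels for someone who stays on one route. For someone who changes route it appears as A1c change that did not happen. The plan recognises that consistency matters but does not enforce it, and the documents give no comparability data for the two routes or the two home kits.

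Randomisation protects the first route but not the later ones. Draws at months 3 and 6 come after allocation, participants know which system they have, and only the Livongo arm has coaching contact. If one arm drifted from one route to the other more than the other arm did, the drift would look like a treatment effect or hide one. A reader could fairly ask for a method term in the primary model, a statement that the method is recorded with each result, and perhaps blocking by route.

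**Working it through.** **Plan's own figures first.** Inputs from section 9.3: difference 0.5, SD 1, two-sided 0.05, 80% power, 150 per arm.

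- n per group = 2(1.960 + 0.842)² / 0.5² = 62.8, so 63 as stated (the exact t-test gives 63.8, so 64).
- Detectable difference at 150 per arm = √(2/150) × (1.960 + 0.842) = 0.323, or 0.325 by the exact t-test. The plan says "the study would have 80% power to detect a minimum effect size of 0.33" (in % A1c), which is consistent. Power at 0.33 is 81.3%, and at 0.5 it is 99.1%.

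**Bias in the month-6 contrast.** Let b be the offset between routes, and d the difference between arms in the net share switching in one direction between baseline and month 6. Bias = b × d. Switches in opposite directions partly cancel. The documents give neither b nor d, so both are assumptions. The last three columns take the bias as running toward the null (power) or as present with no true effect (type I error).

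| b | d | Bias | Share of 0.5 | Power at 0.5 | Power at 0.33 | Type I error |
|---|---|---|---|---|---|---|
| 0.1 | 0.05 | 0.005 | 1% | 99.0% | 80.1% | 5.0% |
| 0.3 | 0.10 | 0.03 | 6% | 98.2% | 73.6% | 5.8% |
| 0.5 | 0.20 | 0.10 | 20% | 93.2% | 51.0% | 13.9% |

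The standard error of the contrast is √(2/150) = 0.115, so the middle case is 0.03/0.115 = 0.26 standard errors.

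**What the last row requires.** If half of each arm starts on each route, one-way switching of 5% v 25% of an arm means 0.05/0.5 = 10% v 0.25/0.5 = 50% of those who began on the route being left. The middle case, 5% v 15%, means 10% v 30%.

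**Similar switching in both arms.** The bias is zero and only noise is added. For a switching share s, the SD of change is √(1 + b²s(1−s)) if all switches go one way, and √(1 + b²s) if directions balance. With b = 0.5 and s = 0.3 these are 1.026 and 1.037. Power at 0.33 falls from 81.3% to 79.3% or 78.5%.

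**Month-3 kit.** A home user who stays on home kits has the professional kit at both baseline and month 6, so a kit offset does not touch that change. At month 3 the arm bias is the kit offset times the difference in home share. Because the first route precedes allocation, that difference is zero in expectation, apart from later switching or missing samples. With half of each arm at home, its chance SD is √(2 × 0.25/150) = 0.058. A kit offset of 0.3 would then add 0.3 × 0.058 = 0.017 of chance error. The shared laboratory gives reason to expect a small kit offset.

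**Would a method term in the primary model help?** In simulation (three visits, half at home at baseline, switching unrelated to true A1c) with offset 0.5 and switching of 5% v 25%, the month-6 bias was 0.101 with no method term. It was 0.101 with baseline route and route by visit only, and 0.001 with actual method. So actual method is the only term that works, and it is measured after randomisation. When the offset was set to zero and switching depended on A1c change in one arm only, the method-adjusted contrast moved by about 0.01 to 0.03, much the same as the middle-case bias it is meant to remove.

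There is also an identifiability problem. With arm, visit, arm by visit, baseline route, route by visit and three-level method, the design has 11 columns and rank 9 when nobody switches. Dropping route by visit leaves 9 columns and rank 8, because baseline route equals the sum of the two home-kit indicators. The arm contrast survives, but the method effect is still not identified.

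**The case for a change.** The strongest case for a change is that an unnamed covariate is chosen after the data are seen, and that a method nobody recorded cannot be adjusted for at all. The trial is open-label, the arms differ in contact, and the outcome affected is the primary one. The remedy looks cheap: one data field and two sentences.

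Part of this stands. Section 7.25 does leave the choice of covariates open, and no sentence says that the collection method is stored with the result. The arithmetic of a switcher's change score is also correct.

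The recording argument is weak in practice. Quest draws run on requisitions sent by the study (sections 7.15, 11.2 and 12.9). Home kits are dispatched for each draw (section 7.9), and results come from two separate companies. The reporting laboratory largely identifies the route, and the scheduled visit identifies the kit. An analyst can therefore tabulate switching by arm and fit a method-adjusted sensitivity model under the existing wording.

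The pre-specification argument cuts both ways. A rule that drops terms when too few participants switch, with no threshold, would itself be settled after seeing the data. Blocking by baseline route would gain almost nothing, because the offset cancels for everyone who stays on that route. A comparison restricted to non-switchers selects on a post-randomisation event and could only be supportive.

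**Conclusion.** No change is needed. The description of the design is accurate, but a wrong result from following the plan requires two things together: a real offset between routes, and net switching that differs by arm. The documents show neither, and they work against the second by strongly asking participants to keep to one route and by obtaining the first sample before allocation.

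On assumed values the likely bias is about 0.03 A1c points (range 0.005 to 0.10), against a planned effect of 0.5. The upper end needs a 0.5-point offset and a 20-point difference in net switching. If switching is similar by arm, the cost is at most about 2 to 3 points of power at 0.33, from a starting point of 81.3%.

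Putting actual method into the primary model exchanges one small possible bias for another of similar size, so leaving the primary contrast free of it is a fair trade-off. What remains is a gap in detail on a form that asks for a brief summary of methods, and the confounder clause in section 7.25 leaves room for analysts to fill it sensibly. This conclusion would need another look if the data showed markedly unequal switching between arms.
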